participant's current pain condition (presence of sciatica), potential prognostic risk for pain-related impairment (e.g., pain catastrophizing, fear avoidance, treatment expectations, and disability/workers compensation), and pain-related service use (e.g., back surgery, injections, opioid and other common prescription medications, various types of exercise, psychological counseling, and use of acupuncture) align with RTF recommendations or are specific to the study's focus on acupuncture. We will measure patient expectations of acupuncture using one item from the EXPECT short form⁶² and using the term acupuncture as the therapy. The question uses a 0 to 10 scale focused on expectations related to acupuncture treatment for chronic low back pain. We will include questions about the impact of the COVID-19 pandemic on the ability to get health care and on their overall health (physical, emotional, and mental, including pain). These were adapted from a patient questionnaire developed by the Pain Management Collaboratory funded by the NIH – Department of Defense and Veterans Administration⁶³. We will ask several questions from the FRAIL scale to characterize participant frailty at the time of enrollment in this study. Finally, we will also collect data from the EHR on other co-morbidities, including various pain conditions. This will allow us to describe the population as well as conduct some moderator analyses.

Aim 1 measures (Baseline AND 3, 6 and 12-monthfollow-up).

Back-related disability will be measured with the 24-item Roland-Morris Disability Questionnaire (RMDQ),⁶⁴ which asked whether 24 specific activities were limited due to back pain during the past week (yes or no). This legacy measure has been found to be reliable, valid and sensitive to clinical changes.⁶⁵⁻⁶⁹ It is appropriate for telephone administration for patients with moderate disability.⁷⁰ The RMDQ will be our primary outcome measure and will be measured as a continuous variable. The minimal clinically important difference (MCID) for the RMDQ in our population is 2 points⁷¹ or 30% improvement from baseline.⁷² The MCID will be examined in a secondary analysis.

As a secondary outcome measure and a HEAL CDE, we will use the PEG scale (a validated, 3-item pain-intensity and pain-related interference composite measure assessing Pain intensity, as well as pain interference with Enjoyment of Life and General Activity).⁷⁵

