For the 6-month time point we will conduct a sequential series of analyses. We will first run a regression model with three groups (acupuncture [SA], acupuncture plus maintenance [EA] and UMC) for the 6-month follow-up. We will then assess differences in change in RMDQ at 6-months between the two acupuncture groups: with (EA) and without (SA) maintenance. If a statistically significant ($\alpha=0.05$) and meaningful difference (>1 point difference) is found between the maintenance (EA) versus no maintenance (SA) groups (Scenario 1), we will further compare each of the acupuncture groups separately to UMC. Scenario 1 assessments will determine if acupuncture with maintenance (EA) is better than acupuncture without maintenance (SA) at 6-months and if either or both acupuncture groups are better than UMC. If acupuncture groups do not differ at 6-months (Scenario 2), we will combine acupuncture groups for this time point and run a second regression model including only UMC and the combined acupuncture group. If this regression model shows that acupuncture is better than UMC, we will conclude that acupuncture improved RMDQ at 6-months, but maintenance was not shown to be efficacious.

We will follow the same general framework for 12-month as we have specified for 6-months. Note that the analysis focused on the 12-month follow-up timepoint provides an important test of whether maintenance (EA) makes an appreciable difference over standard acupuncture in sustaining or improving the effect of acupuncture on pain-related functioning that endures after the end of treatment. Finally, note that we include all time points in a single model within this general modeling framework to handle correlation due to multiple outcomes on a given person.

To control for multiple comparisons when testing between the three groups at 6-months we will use Fisher's least significant (LSD) difference procedure.¹⁰² Fisher's LSD has been shown to strongly hold the family-wise error rate at α -level for studies with three treatment groups.¹⁰³ Fisher's LSD is a simple procedure where the global Wald-test of the null hypothesis of equal means for all groups is performed first. If this overall test is statistically significant then the sequential series of pairwise comparisons will be performed as outlined previously; otherwise the procedure stops, failing to reject the over null hypothesis that at least one mean is different

from the others.

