The above power calculation was conducted with RMDQ score as the outcome. When the outcome of interest is the change on RMDQ score from baseline to 6-month, we expect a smaller SD than 6 points in each arm (based on previous trial data conducted at KPWHRI only the SD RMDQ at 6 months was 5.42 and change in RMDQ was 5.11). Thus, we are sufficiently powered ( $\geq 90\%$ ) to detect MCID differences between all pairwise group comparisons. Power was calculated via simulation using R software version 3.6 accounting for multiple comparisons of the three study arms using Fisher's Least significant different approach. Note to be conservative we assumed a larger SD than we expect since we may have loss to power due to clustering of participants within acupuncture provider (acupuncturists may see 10-15 participants) and we may have more variability in baseline outcome since this trial is pragmatic across four health care systems. Inflating the SD by more than 15% ( $6/5.11=1.17$ ) should take into account both potential loss to power issues. Furthermore, although acupuncturists may see up to 10-15 participants at our smallest site (IFH) this accounts for 16% of our expected recruited sample (123 of 789 with only two-thirds of those randomized to an acupuncture arm where clustering is of issue). At other sites, the combination of HCS embedded and community acupuncturists are expected to result in much smaller caseloads (3-8 participants on average). In keeping with a pragmatic trial approach and to lower barriers to participant receipt of acupuncturists, we are motivated to include a larger number of acupuncturists serving participants in the study

For any two group comparisons, given our sample size of 210 per group and a SD of 6, the 95% CI width around the difference in means between groups is +/- 1.15 pts. Further, for secondary analysis for the binary outcome 30% improvement in RMDQ from baseline we have >90% power to detect an MCID assuming the probability of improvement in UMC was between 33%  and 44%  and the MCID was a 15% improvement above UMC for each of the acupuncture groups. We will use an intent-to-treat approach in which participants will remain as randomized regardless if they withdrawal from treatment or cross-over to other treatment arm (e.g. UMC participant seeks acupuncture outside of study).

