## **8. Multiple Comparisons**

We have one primary outcome – the change on RMDQ scores for low-back pain related disability at 6 months since baseline. To control for multiple comparisons due to 3 intervention groups we will apply Fisher's Least Significant Difference approach in which first an omnibus Wald-test for any statistically significant difference

between the three groups is evaluated at the 0.05 alpha level. If the omnibus test is statistically significant, then the pair-wise differences are then evaluated, each using two-sided alpha=0.05. If the omnibus test is not statistically significant, we will conclude that there is no benefit of acupuncture for that time point. In addition, secondary analyses will use a similar approach as that described for the primary outcome to control for the three group comparisons.

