## 13. Effectiveness Analyses on Changes in RMDQ Scores

We will evaluate the effectiveness of acupuncture and acupuncture plus maintenance relative to Usual Medical Care (UMC) at 3-, 6- (primary time-point), and 12-months after randomization. We will conduct a longitudinal analysis including the continuous outcome, change in Roland Morris Disability Questionnaire (RMDQ) from baseline (primary outcome) measured at all follow-up times, in one model estimated using generalized estimating equations (GEE).  We will use a working independence correlation matrix and will calculate standard errors using the robust sandwich estimator to account for within-person and within-in provider (some participants may see the same provider) correlation. All models will adjust for baseline RMDQ score, age, sex, race and HCS. Further, if missing RMDQ at 6 months (primary time point) is more than 15% in any study arm, or differential by more than 10% between any two arms, we will use imputation approaches as the primary analysis to account for missing data and further adjust for any baseline variables that are predictive of loss to follow-up determined as described in Section 9. All analyses will be conducted following an intent-to-treat approach, including all individuals randomized regardless of their engagement with, or exposure, to the intervention.

We will include interactions between intervention groups and time (3-, 6-, and 12-months) to estimate time-specific intervention effects. Time will be included as a categorical variable. To gain power, since acupuncture and acupuncture plus maintenance at 3-months are the same intervention (maintenance period occurs between 3 and 6 months post randomization and neither participants in the EA condition nor the acupuncturists treating them will be aware they will receive maintenance treatments until close to the 3-month follow-up), we will combine acupuncture groups at 3-month follow-up. We chose GEE as our analytic method because our primary outcome, RMDQ, is not expected to be normally distributed. From our experience working with RMDQ data, adjusting for baseline RMDQ value results in more normally distributed residuals. However, we didn't want to make that assumption a priori and therefore chose GEE.

Our specific model for change in RMDQ is the following:

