### 13.2 Secondary Time Points: 3- and 12-Months Post Randomization

The acupuncture's impact on the change of RMDQ scores at 3-months will be assessed by testing if  $\beta_{Acu} = 0$  in equation (1) since acupuncture and acupuncture plus maintenance at 3-months are the same intervention (maintenance period occurs between 3 and 6 months post randomization and neither participants in the EA condition nor the acupuncturists treating them will be aware they will receive maintenance treatments until close to the 3-month follow-up). We will follow the same general framework for 12-months as we have specified for 6-months in Section 13.1. Note that the analysis focused on the 12-month follow-up timepoint provides an important test of whether EA makes an appreciable difference over SA in sustaining or improving the effect of acupuncture on pain-related functioning that endures after the end of treatment. Finally, note that we include all times points in a single GEE model within this general modeling framework to handle correlation due to multiple outcomes on a given person. We will report both the fully saturated model 1 results and an additional final model if scenario 2 is correct for either 6 or 12 months. For example, if scenario 2 is concluded for both time points 6 and 12 months the final model is:

Scenario 2 is correct for 6 and 12 months:

$$(2) \quad E(Y_{im}|T_i, Z_i) = \alpha + \beta_{Acu}I(T_i = SA \text{ or } EA) + \beta_z Z_i + \beta_6 I(m = 6) + \beta_{12} I(m = 12) \\ + \gamma_{Acu,6} I(T_i = SA \text{ or } EA)I(m = 6) + \gamma_{Acu,12} I(T_i = SA \text{ or } EA)I(m = 12).$$

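### SAP section 8 turns a non-significant omnibus test at 6 or 12 months into a conclusion of no benefit, even when an acupuncture-versus-usual-care interval still contains the 2-point MCID

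*SAP*

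**What the plan says.** SAP section 8 (Multiple Comparisons) uses Fisher's LSD. A three-group Wald test is done at the 0.05 level, and pairwise tests at two-sided 0.05 follow only if it is significant. For the other branch it says: "If the omnibus test is not statistically significant, we will conclude that there is no benefit of acupuncture for that time point". The section then extends a similar approach to the secondary analyses, and SAP section 13.2 applies the 6-month framework at 12 months.

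Protocol section 9.6 describes the same branch more weakly: "otherwise the procedure stops, failing to reject the over null hypothesis that at least one mean is different". That phrase misstates the null. Earlier in the same paragraph the null is given correctly: "the global Wald-test of the null hypothesis of equal means for all groups is performed first".

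Three other statements matter:
- Protocol section 6.2.2 (Aim 1 measures): "The minimal clinically important difference (MCID) for the RMDQ in our population is 2 points". It gives 30% improvement from baseline as an alternative.
- SAP section 4, for 210 per group and SD 6: "the 95% CI width around the difference in means between groups is +/- 1.15 pts".
- SAP section 13.2, on reporting: "We will report both the fully saturated model 1 results and an additional final model if scenario 2 is correct".

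At 3 months the rule does not operate, because "we will combine acupuncture groups at 3-month follow-up" and a single parameter is tested.

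**The concern.** A non-significant 2-df test means that the data did not separate the three means at the 5% level. Whether a worthwhile benefit has been excluded depends on the estimates and their intervals, and section 8 does not refer to them. As written, an inconclusive result at the primary time point must be reported as a negative one.

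The protocol (section 2.2) says that the trial will inform Medicare's coverage decision and the choices of physicians and patients. Those readers could be told that acupuncture has no benefit when the trial's own interval still contains the difference that the documents call clinically important. SAP section 13.2 means that the model 1 estimates will be shown, but nothing links them to the conclusion that section 8 prescribes.

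**Working it through.** **Inputs.** 210 analysed per arm and SD 6 (SAP section 4). SD of change 5.11 from an earlier trial (SAP section 4: "only the SD RMDQ at 6 months was 5.42 and change in RMDQ was 5.11"). Omnibus alpha 0.05 on 2 df, critical value 5.991. MCID 2 points. Arm variances are taken as equal; covariate adjustment and clustering by acupuncturist are not modelled.

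**1. The SAP's precision figure reproduces.** Half-width = 1.96 × SD × √(2/210).
- SD 6: 1.148, which matches the stated 1.15.
- SD 5.11: 0.977.

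**2. When a pairwise interval reaches 2 points.** The estimate must be at least 2 − 1.148 = 0.85 (SD 6) or 2 − 0.977 = 1.02 (SD 5.11).

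**3. When the omnibus test is non-significant.** Q = (210/SD²) × Σ(arm mean − average of the three)², compared with 5.991.
- SA and EA both at d: Q = (210/36)(2/3)d² = 3.889d², non-significant for d up to 1.24 at SD 6.
- One arm at d, the other at d/2: Q = (210/36)(1/2)d² = 2.917d², non-significant for d up to 1.43.

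So at SD 6 there is a band of estimates, 0.85 to 1.24 or 0.85 to 1.43, where the test fails and the interval still includes 2. At SD 5.11 the bands are 1.02 to 1.06 and 1.02 to 1.22.

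**4. Examples.** On 2 df, p = exp(−Q/2).
- SD 6, SA 0.7, EA 1.3: the average is 0.667 and the squared deviations sum to 0.4444 + 0.0011 + 0.4011 = 0.8467. Q = 5.833 × 0.8467 = 4.94, p = 0.085. EA versus UMC: 1.3 ± 1.148 = 0.15 to 2.45.
- SD 5.11, SA 0.6, EA 1.15: the squared deviations sum to 0.6617. Q = 8.042 × 0.6617 = 5.32, p = 0.070. EA versus UMC: 1.15 ± 0.977 = 0.17 to 2.13.

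**5. How often.** Simulation with equal true benefit in both arms, 4 million runs. The last column is the product of the two before it.

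| SD | True benefit | P(omnibus non-significant) | P(at least one CI includes 2, given non-significant) | Joint |
|---|---|---|---|---|
| 6 | 1.0 | 0.595 | 0.598 | 35.6% |
| 6 | 1.5 | 0.242 | 0.796 | 19.2% |
| 6 | 2.0 | 0.0485 | 0.905 | 4.4% |
| 5.11 | 1.0 | 0.466 | 0.249 | 11.6% |
| 5.11 | 1.5 | 0.115 | 0.406 | 4.7% |
| 5.11 | 2.0 | 0.0099 | 0.532 | 0.5% |

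The joint share in which at least one such nominal interval also excludes zero is 16%, 10.5% and 2.8% at SD 6. At SD 5.11 it equals the last column, because an estimate large enough to reach 2 (1.02) already exceeds the half-width (0.977). Both intervals doing so is rare, under 1% at SD 6.

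**6. Three months.** Assuming the same 210 per arm, the pooled contrast has SE = 6 × √(1/210 + 1/420) = 0.507. A non-significant estimate is below 1.96 × 0.507 = 0.994, so its upper limit is at most 2 × 0.994 = 1.99. The conflict does not arise there under SD 6, though the margin is thin.

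**The case against.** The strongest reply is that this is loose wording rather than a faulty analysis. Protocol 9.6 speaks only of failing to reject, and SAP 13.1 says of the parallel SA-EA comparison that maintenance was not shown to work. The model 1 results will be printed, so nothing is hidden. The conflict is also uncommon when acupuncture works as powered: 4.4% (SD 6) or 0.5% (SD 5.11) with 2 points in both arms, and 3.4% or 0.3% in the SAP's other scenario, where SA equals UMC and EA is 2 points better. The larger shares need a true benefit below the MCID, and the SAP calls SD 6 larger than it expects.

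Much of this is fair on size. The percentages measure overlap of an interval with 2 points; the replacement text would reword the conclusion of every non-significant trial. The intervals excluding zero are nominal. Under Fisher's LSD they support no claim once the gate has failed, and none is made here. The documents do not name 2 points as a margin for ruling out benefit, and they give a 30% improvement as an alternative MCID.

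The core is not answered. Section 8 prespecifies a conclusion, and the weaker wording elsewhere does not qualify it; it shows that the documents disagree. Printing an interval up to 2.45 beside a conclusion of no benefit leaves the report contradicting itself. SD 6 is the SAP's chosen planning value, set partly to allow for clustering.

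**Conclusion.** The concern holds. Section 8 draws an affirmative conclusion that a non-significant omnibus test cannot support, at the primary time point and at 12 months, and it goes further than Protocol 9.6. At the planning SD of 6 the rule conflicts with at least one of the trial's own intervals in 36%, 19% and 4.4% of trials for true benefits of 1.0, 1.5 and 2.0 points in both arms. At SD 5.11 the figures are 12%, 4.7% and 0.5%. They rest on 210 analysed per arm, equal variances, and no covariate adjustment or clustering; larger standard errors would widen the overlap.

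The Fisher gate is not at fault. The type II error of the omnibus test (59%, 24% and 5% at SD 6) is not the harm claimed, and the fix leaves it unchanged. The fault is the conclusion attached to the gate. It should be corrected but calls for no redesign. The misworded null in Protocol 9.6 is an editorial slip.

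**What to change.** Replace the sentence in SAP section 8 with:

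> If the omnibus test is not significant, no claim of superiority is made for that time point; the SA-UMC, EA-UMC and EA-SA estimates with 95% CIs from model 1 are reported. For RMDQ, absence of a clinically important benefit is stated only if the 95% CIs for both SA vs UMC and EA vs UMC exclude a 2-point improvement.

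For secondary outcomes only the first sentence applies. That sentence cures the main defect on its own; the second says when a negative conclusion is earned, using the documents' own RMDQ MCID. In Protocol 9.6, reword the later phrase so that the null is equal means, as stated earlier in the same paragraph.

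The cost is two sentences in the SAP and one phrase in the protocol. The model, alpha, gate, power and sample size do not change, and the estimates are already planned output.

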## 9. Missing Data

The investigators and data managers will monitor data collection process on a weekly basis and ensure a minimal amount of loss to follow-up in the study. All analyses will be conducted following an intent-to-treat approach, including all individuals randomized regardless of their engagement with, or exposure, to the intervention. If missing data for RMDQ is minimal, our primary analysis will be a complete case analysis adjusting for baseline RMDQ score, age, sex, race and HCS. If missing data for RMDQ at 6 months is above 15% in any arm, or differential by 10% between any two arms, then for our primary analysis we will employ missing not at random imputation techniques to address missing data issues. Though the metric used to make decisions about the analysis method focuses on missing data at the primary time point (6 months), if criteria are met missing data will be imputed 3, 6 and 12-month time points. However, our focus will be on minimizing missing data, and in our collective substantial experience conducting similar trials, we have consistently had retention in line with this. Should it be necessary, the imputation method we propose, derived for use with GEE and sensitive to potential non-ignorable missingness, includes all follow up time points in the same model and uses a pattern mixture approach that relaxes the missing at random given baseline covariates assumption. This accomplished via the implementation of an imputation model which includes indicators classifying the mutually exclusive missing data patterns observed across all time points in the data. We will describe all of the missing data patterns present in the observed data to identify a scientifically reasonable and estimable set of patterns to use as indicators in imputation models for each outcome. Specifically, following the recommendations of Wang and Fitzmaurice, we plan to use the most flexible (parameterizing the largest number of missing patterns) that are estimable with the data. We will construct the imputation models such that the effects of missing data on the outcome are allowed to vary by treatment arm and follow-up time and will include main effects for all covariates used as stratification factors in the study randomization and/or thought to be potential confounders of the relationship between outcome and treatment arm. Further, we will include additional baseline variables that are predictive of missing the 6 months outcome. Specifically, baseline covariates that are significantly (at 0.10 significance level) associated with missingness at 6 months using flexible logistic regression models will be included as main effects in imputation models.

Following imputation of the data using the models described here, final effect estimates will be obtained in the full imputed data using GEE with the functional model form described in section 13 below, where the vector of covariates,  $Z$ , includes stratification variables, potential confounders and variables identified as being significantly associated with missingness. Standard error estimates will be calculated using the sandwich-style estimator derived by Wang and Fitzmaurice, which takes into account variability due to imputation and is shown to provide consistent estimates of the true standard errors. It is an extension of the standard GEE model which is incorporating the variability due to multiple time points and acupuncturists as proposed in our primary analysis model (see Section 13), but adds imputation to relax the missing at random given baseline covariates assumption of standard GEE. Because the sites participating in this study represent multiple disparate health systems each with its own unique member populations, culture, guidelines, and practices, we will conduct a sensitivity analysis allowing the effect of potentially non-ignorable missing data patterns to vary by site and treatment group at each follow-up time point instead of just including site indicators as main effects in the imputation model. Further sensitivity analyses related to the choice of missing data patterns will be considered as necessary.

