We will conduct a similar analysis for secondary and tertiary outcomes, including key secondary outcomes such as the PEG and will use appropriate link functions for non-continuous outcomes. All models will adjust for baseline outcome value, age, sex, and HCS as well as any baseline variables that are predictive of loss to follow-up. All analyses will be conducted following an intent-to-treat approach, including all individuals randomized regardless of their engagement with, or exposure, to the intervention. If loss to follow-up is above 15%, we will employ imputation techniques to address missing data issues.¹⁰⁴ However, our focus will be on minimizing loss to follow-up and in our collective substantial experience conducting similar trials, we have consistently had retention in line with this. The imputation method that we were referencing uses a pattern mixture approach that relaxes the missing at random assumption. This approach that we propose using is derived for GEE and is sensitive to potential non-ignorable missingness.¹⁰⁴

Exploratory analyses will further use tertiary outcome data collected monthly (i.e., the PEG and PROMIS®, Physical Function). We will use these measures to assess the trajectory of how long it takes until patients improve and to address questions such as “What proportion of people improve at three months if they don’t improve after one or two months of acupuncture?” These exploratory analyses will help address how much acupuncture is needed to improve and at what time, given a patient’s outcome trajectory, should acupuncture treatment stop if improvement has not been shown up to that time.

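### When neither missing-data trigger is met, the primary 6-month comparison ignores what dropouts reported earlier, has no missing-data sensitivity analysis, and can be biased if dropout follows early response differently by arm

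*SAP*

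**What the plan says.** SAP section 9 has two branches. If little RMDQ is missing, "our primary analysis will be a complete case analysis adjusting for baseline RMDQ score, age, sex, race and HCS". The other branch opens with "If missing data for RMDQ at 6 months is above 15% in any arm, or differential by 10% between any two arms" and makes a pattern-mixture imputation, which allows non-ignorable missingness, the primary analysis. Protocol 9.6 has only one limb: "If loss to follow-up is above 15%, we will employ imputation techniques to address missing data issues".

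SAP section 13 describes the model for both branches: "We will use a working independence correlation matrix", with robust standard errors for person and provider, and "We will include interactions between intervention groups and time (3-, 6-, and 12-months) to estimate time-specific intervention effects". On covariates it says "All models will adjust for baseline RMDQ score, age, sex, race and HCS", and it adds baseline predictors of loss only if the trigger is met. Protocol 9.6 lists age, sex, HCS and baseline outcome for all models "as well as any baseline variables that are predictive of loss to follow-up", with no trigger.

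Section 9 also states that standard GEE assumes data missing at random given baseline covariates. Its sensitivity analyses (pattern effects varying by site, other choices of pattern) concern the imputation model. None is described for the complete-case branch. PEG and physical function are collected monthly (Protocol 6.2.4) but serve only exploratory analyses (Protocol 9.5.3, SAP section 17).

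**The concern.** Someone who misses the 6-month survey may already have given a 3-month RMDQ and PEG and physical function at months 1, 2, 4 and 5. Those scores are the best information available on how that person was doing, and below the trigger the primary contrast sets them aside.

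Participants know whether they have acupuncture, and SA or EA status is disclosed at about week 10. In months 4-6 EA participants attend maintenance visits and SA participants do not. It is therefore conceivable that reasons for not answering differ by arm. The trigger counts missing outcomes, so it cannot see who is missing. Two arms can lose equal shares below 15%, one losing people who did badly and the other people who did well. The primary estimate would then shift with no planned analysis to show it. The same applies to SA versus EA, the first step of the 6-month sequence, which uses a significance test and a rule of more than 1 point.

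**Working it through.** **Inputs from the documents.** 263 randomized and 210 completers per arm; 20% planned loss; SD 6; 2-point MCID (SAP section 4); trigger limbs of 15% and 10% (SAP section 9); a rule of more than 1 point (SAP 13.1).

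**Assumed inputs.** The documents give neither the correlation between visits nor a dropout mechanism. I take equal correlation ρ between visits of 0.5-0.75, odds of missing month 6 multiplied by about 2 (logistic slope 0.7) per SD of 3-month RMDQ, and a true effect of -2 points.

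**Step 1: the plan's figures reproduce.** 210/0.80 = 262.5, so 263 per arm. The 95% half-width is 1.96 × 6 × √(2/210) = 1.15. Simulated power under the omnibus-then-pairwise rule is 91%.

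**Step 2: what the 6-month contrast uses.** Model (1) leaves the 6-month means of UMC, SA and EA free of each other. Under working independence each is fitted to the 6-month records alone, apart from the covariate slopes, which are shared across visits. A person with no 6-month record contributes only through those slopes.

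**Step 3: size by hand.** If a fraction m is missing and dropouts lie d SDs above their arm's mean at month 3, completers lie d·m/(1-m) below it. After adjustment for baseline, the 3-month score carries ρ - ρ² = ρ(1-ρ) of an SD into month 6. So the shift in one arm is about

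SD × ρ(1-ρ) × d × m/(1-m).

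At m = 14% and slope 0.7, simulation gives d ≈ 0.57, and m/(1-m) = 0.14/0.86 = 0.163.

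- ρ = 0.50: 6 × 0.250 × 0.57 × 0.163 = 0.14
- ρ = 0.65: 6 × 0.2275 × 0.57 × 0.163 = 0.13
- ρ = 0.75: 6 × 0.1875 × 0.57 × 0.163 = 0.10

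A link in one arm leaves this as bias. Opposite links double it, to 0.21-0.28. A common link at a common rate cancels.

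**Step 4: simulation.** Large-sample estimates, SD 6, ρ 0.5-0.75, true effect -2:

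| Dropout | Missing | Complete case | Using 3-month RMDQ |
|---|---|---|---|
| Opposite links (UMC non-improvers, acupuncture improvers) | 14% and 14% | -1.72 to -1.78 | -1.99 to -2.00 |
| UMC non-improvers only | 14% and 12% | -1.86 to -1.90 | -1.99 to -2.02 |
| Same link, relative to arm mean | 14% and 14% | -2.00 | -1.99 to -2.00 |

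In 1,500 trials of 263 per arm at ρ = 0.65, complete case gave -1.73, -1.87 and, with no link at all, -2.01.

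**Step 5: other assumptions.** Suppose the correlation (0.5-0.7) and SD (5.11-6) are those remaining after baseline is accounted for. The shift is then SD × ρ × d × m/(1-m). At 14.9% missing, d is about 0.56, so the upper value is 6 × 0.7 × 0.56 × 0.149/0.851 = 0.41. Simulated bias in absolute points:

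- link in acupuncture only: 0.10-0.17 at 5% missing, 0.16-0.29 at 10%, 0.24-0.41 at 14.9%
- same slope but 5% versus 14.9% missing, just inside the 10% limb: 0.18-0.25
- opposite links at 14.9%: 0.49-0.81
- one common rule acting on absolute 3-month change, about 12% missing: 0.04-0.11, toward the null

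With SD 5.11, correlation 0.6 and 14.9% missing, the null pairwise rejection rate without the omnibus gate was 5.1% (common link), 9.3% (one arm) and 23.8% (opposite).

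**Step 6: effect on power in the Step 4 case.** 263 × 0.86 = 226 completers per arm. At SD 6 the standard error is 6 × √(2/226) = 0.564, and ungated pairwise power falls from 94% at 2.00 to 87% at 1.73. With the baseline-adjusted SD, 6 × √(1 - 0.65²) = 4.56, it falls from 99.7% to 98.1%.

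**The case against.** A reader might infer that dropout linked to early response biases the effect as such. The documents do not support that, and neither do the calculations: the same link in every arm, relative to the arm mean, gives about 0. Nor is it true that complete case needs missingness to depend on nothing beyond the listed baseline covariates. Arm is in the model, so missingness may also depend on arm.

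The branch is narrower than a 15% rule suggests. The 10% between-arm limb catches many arm-differential cases, though not opposite mechanisms at similar rates. The plan's own 20% loss would trigger imputation. Against that, the SAP says retention in similar trials has been consistent with its missing-data target, so complete case may well be the analysis that is used.

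The mechanism is plausible but not documented. Stopping treatment is not the same as missing the outcome: Protocol section 8 asks those who stop to continue assessments, and outcomes are collected centrally by masked interviewers or by web, with reminders and incentives. This makes a strong link less likely but does not exclude it. The shift of 0.27 points in the opposite-link case is also small beside the 1.15-point half-width.

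Two further inferences should be resisted. One is that the imputation branch also ignores a person's own RMDQ. SAP section 9 names pattern indicators and baseline covariates ("Further, we will include additional baseline variables that are predictive of missing the 6 months outcome"), but it also says all follow-up times enter one model. Whether observed RMDQ is conditioned on cannot be settled from the documents. The other is that MAR imputation should replace the primary analysis above the trigger. That would reinstate the assumption the plan set out to relax. The good performance of the MAR estimator in Step 4 follows from generating missingness from the 3-month score. When missingness depended on the 6-month score itself, in opposite directions, complete case gave -1.33 and the MAR estimator -1.42 against -2.

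**Conclusion.** The point holds in a limited form. Below both trigger limbs, the primary 6-month contrast discards relevant data already collected and has no planned check on the missing-data assumption. It can be biased when the link with early response differs by arm: about 0.1-0.15 points for one arm and 0.2-0.3 for opposite links on a 2-point effect, under the inputs assumed in Step 4. Step 5 shows that other assumptions reach 0.4 and 0.8 points. Size and direction therefore rest on assumptions the documents cannot supply. With a common link the bias is about 0, or at most 0.11 if dropout follows absolute change.

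Separately, Protocol 9.6 and SAP section 13 disagree on whether baseline predictors of loss enter the model below the trigger. That needs reconciling in its own right, because baseline adjustment does not address dropout driven by early response.

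**What to change.** For the below-trigger branch only:

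1. Pre-specify an analysis that handles missing RMDQ under MAR, separately by arm, with the participant's observed RMDQ at other visits and monthly PEG and physical function in the imputation model. Follow it with the same GEE and provider-robust standard errors. At a minimum, make it the named sensitivity analysis whenever complete case is primary.
2. Restore Protocol 9.6's adjustment for baseline predictors of loss in this branch, so that the protocol and SAP section 13 agree.

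Leave the pattern-mixture primary above the trigger unchanged.

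The cost is SAP wording, modest programming and one more modelling step to report. No new data are needed and the sample size stays at 263 per arm. When missingness is unrelated to early response the two analyses should agree. The change does not correct missingness that depends on the unobserved 6-month score.
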